3.1 Stratification Factors

The randomization will be stratified by response per investigator at completion of CHOP-based therapy (CR vs PR).

3.2 Sample Size Considerations

A total of approximately 549 randomized patients are planned for this study.

Outcome data for patients with T-cell lymphoma who receive first-line CHOP are limited. A retrospective study of the International T-Cell Lymphoma Project demonstrated a 5-year overall survival (OS) rate of 32% and a 5-year failure-free survival (FFS) rate of 20% for patients with peripheral T-cell lymphoma unspecified (PTCL-U), with widely varying results for other subtypes.¹ Median OS for these patients did not seem to be a function of whether the patient received an anthracycline-based induction therapy. In a retrospective evaluation of 96 patients diagnosed within the Non-Hodgkin's Lymphoma Classification Project, Rudiger et al report a similar finding, with 5-year OS and FFS rates of 26% and 20%, respectively, for PTCL patients treated with a doxorubicin-containing regimen.² Per Figure 1 of the Rudiger publication, the estimated median FFS in these patients is approximately 6 months.

Reports of response rate to first-line CHOP-based regimens in patients with PTCL are also available. Gallamini et al, conducted a small study (n = 24 evaluable) evaluating CHOP plus alemtuzumab administered every 4 weeks for a total of 28 weeks.³ They observed an overall response rate of 75% (71% CR, 4% PR). In a separate report, Gallamini et al, performed a retrospective analysis of 385 patients with PTCL-U, with the majority (78%) receiving chemotherapy containing anthracycline.⁴ They reported an overall response rate of 74% (53% CR, 21% PR) in the 372 evaluable patients. Mercadal and colleagues reported on

a series of 41 patients ≤ 65 years old who were planned to receive 6 cycles of intensive chemotherapy (high-dose CHOP alternating with etoposide, methylprednisolone, cytarabine, and cisplatin [ESHAP]) followed by autologous stem cell transplantation if in response.⁵ Twenty-eight patients (68%) received the planned 6 courses of therapy, 6 patients (15%) received 5 courses of therapy, and 7 (17%) received less than 5 courses. Following the chemotherapy phase, the CR rate was 49% and the PR rate was 10%. Kim and collaborators administered CHOP plus etoposide and gemcitabine to a cohort of 26 first-line PTCL patients.⁶ The median number of cycles administered was 4, and the overall response rate was 77% (62% CR, 15% PR). Abouyabis and colleagues performed a meta-analysis of non-anaplastic large cell lymphoma (ALCL) PTCL patients receiving anthracycline-based chemotherapy in the first-line setting.⁷ A total of 31 studies were identified involving a total of 1996 patients. The overall CR rate was 55% and the 5-year OS rate was 37%.

Across all of these reported studies, approximately 50% of patients achieve a CR to first-line CHOP, with an additional 10-20% achieving a PR. Furthermore, the 5-year progression-free survival (PFS) is approximately 20%, with a median PFS of approximately 9 months in all patients. For sample size calculations for the PDX-017 study, we assume that one-third of these patients will have disease refractory to CHOP and that the median PFS in these patients will be 3 months. Coupled with an overall median PFS of 9 months, and assuming exponentially distributed PFS, this implies the median PFS in patients who respond to CHOP is approximately 16 months. Subtracting out 6 months for CHOP administration and washout prior to randomization results in an estimated 10-month median PFS for Observation Arm patients in PDX-017.

The sample size is based on comparing the treatment groups with respect to the primary efficacy endpoints of PFS and OS. Assuming proportional hazards, a true hazard ratio (HR) on OS of 0.73, and a 2:1 randomization (treatment:observation) with a total of 549 patients (366 in the treatment group vs 183 in the observation group), a total of 385 OS events (deaths) will provide at least 80% power to show $HR < 1.00$ using a 2-sided stratified log-rank test at a 0.05 significance level ($\alpha = 0.05$), assuming an accrual period of 54 months and a follow-up period of 30 months. For a HR on PFS of 0.67, a total of 280 PFS events (PD + deaths) will provide at least 80% power to show $HR < 1.00$ using a 2-sided stratified log-rank test at a 0.05 significance level.

Further assuming that PFS is exponentially distributed, that the median PFS in the control group is 10 months, and that uniform enrollment will occur over 54 months, under the alternative hypothesis that $HR = 0.67$, the 280th event will occur approximately 48 months after the first patient is randomized. Allos will set a data cut-off date for the primary efficacy analysis in anticipation of the 280th PFS event and 128th OS event.

3.3 Interim Analyses

A step down procedure will be used for analyzing the co-primary endpoints of PFS and OS. If the PFS endpoint is significant at the 0.05 level the OS endpoint will be tested at an overall significance level of 0.05. However, if the PFS endpoint fails to show significance, the study will be stopped and OS will not be tested. The study will meet its primary objective if both

the PFS and OS endpoints are significant. The interim analyses for OS will be implemented using the error-spending approach of Lan and DeMets according to the unified family approach with boundary relationships of O'Brien and Fleming for early stopping to reject the null hypothesis (superiority).^{8,9} The boundaries for early stopping due to failure to reject the null hypothesis (futility) will be determined according to the unified family approach with boundary shape parameters on the sample mean scale that result from choosing $P = 2.0$ (all R and A parameters in the unified family approach set equal to zero).¹⁰

There will be 1 final analysis of PFS, and 2 interim and 1 final analyses of OS. The first interim analysis of OS will be performed at the same time as the PFS analysis. The first interim analysis will be performed when both 280 PFS events and 128 OS events have occurred. The only analysis for PFS will be performed at this first analysis point, at the 0.05 level of significance. If PFS is significant at the 0.05 level, the first interim analysis will be conducted on survival at this time. If the PFS analysis is not significant at the 0.05 level, the study will be stopped. If there are 128 OS events, or one-third of the information of 385 deaths, included in the first interim analysis of OS, the level of significance (alpha) would be 0.0002, according to O'Brien and Fleming.^{8,9} If PFS is significant, a test for futility of OS will not be conducted at the first interim analysis since such a result could not occur. The second interim analysis for OS will be performed when two-thirds (256) of the survival events have occurred, at the 0.013 level of significance. The HR stopping bound for futility at this interim analysis will be 1.05 (95% confidence interval [CI]: 0.80, 1.29). If the HR for OS is greater than 1.05, the study will be stopped. The final analysis for survival will be performed when 385 OS events have occurred, at the 0.046 level of significance.

The stratified log-rank test (stratified by response to prior CHOP-based therapy) will be the primary method used to test the hypothesis that pralatrexate extends PFS and OS relative to observation. In addition, the stratified Cox regression model will be used to calculate the PFS and survival hazard ratio (HR), along with their 95% CIs. Results of the unstratified Cox regression model (and log-rank test) will also be presented. The proportional hazards assumption of the Cox model will be assessed.

Data Monitoring Committee

A Data Monitoring Committee (DMC) will evaluate safety after approximately 100 patients have been randomized and have completed at least 8 weeks post-randomization pralatrexate/observation or have discontinued. Safety evaluations will also be performed at the same time of each interim analysis of efficacy. All interim analyses will be performed by the DMC.

At each interim analysis for survival, the DMC will make a recommendation to Allos to either stop or continue the study. The study could be stopped for overwhelming evidence of superiority or futility according to specified boundaries. At the first interim analysis for survival, the DMC could also make the recommendation to Allos to submit a regulatory filing based on positive results of the PFS endpoint plus a trend of survival in favor of the pralatrexate treatment group. Allos may discuss the DMC's recommendations with

regulatory authorities before any such action is taken. The DMC may also make recommendations regarding adjustments to the sample size, if they are warranted.

4 STUDY ENDPOINTS AND COVARIATES

4.1 Primary Efficacy Endpoints

The co-primary efficacy endpoints are PFS and OS.

4.2 Secondary Efficacy Endpoint

The secondary efficacy endpoint is objective response (CR or PR) to pralatrexate versus observation.

The primary analyses of PFS and objective response at the first interim analysis will use the central review of tumor assessments per International Workshop Criteria (IWC) without positron emission tomography (PET). Additional analyses of PFS and objective response will use IWC, including PET, and investigators' assessment of response. Additional details regarding central review will be provided in the reviewer's charter.

4.3 Safety Endpoints

Safety endpoints include:

- Incidence and severity of treatment-emergent adverse events (AEs).
- Changes in laboratory values.

4.4 Potential Covariates

The following covariates will be considered in covariate-adjusted and other exploratory analyses:

- Stratification factor (CR vs PR to prior CHOP-based therapy);
- The International Prognostic Index (IPI) score at initial diagnosis (plus individual components as collected);
- Histology (PTCL-U vs transformed mycosis fungoides vs ALCL vs other); and
- Region.

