### 10.1 Screening

The procedures and evaluations required for randomization are summarized below. Randomization of eligible patients must occur within 6 weeks of day 1 of the last planned cycle of CHOP-based chemotherapy.

1. Review eligibility criteria.
2. Obtain written IC for pathology review prior to sending pathology specimen(s) to independent pathology reviewer.
3. Send the pathology specimen(s) to independent pathology reviewer (see [Section 12.2.2](#)). Independent pathology review of tumor tissue specimens and confirmation of diagnosis must occur prior to randomization and can occur any time after the initial PTCL diagnosis, provided that the patient has consented to the pathology review.

Unless otherwise specified, the following procedures and evaluations will be performed within 21 days prior to randomization:

1. Obtain written IC for participation in this study prior to initiating any study procedure that is not considered standard of care.
2. Review eligibility criteria.
3. Review medical chart and record medical/surgical history.
4. Document histopathology from local pathology report.
5. Document IPI score at initial diagnosis.
6. Record baseline/current medical status, including B symptoms related to PTCL.
7. Document dates of CHOP-based chemotherapy.
8. Document the investigator's assessment of response after receipt of CHOP-based chemotherapy.
9. Document known measurable disease parameters by obtaining the following radiographic imaging:
  - Computed tomography (CT) of chest, neck, abdomen, and pelvis (magnetic resonance imaging [MRI] allowed if the patient cannot tolerate the IV contrast).
  - Other imaging techniques documenting disease site other than chest, neck, abdomen, and pelvis, if applicable.
10. Perform whole body positron emission tomography (PET) (base of skull to mid-thigh) if local standard of care.
11. Document cutaneous disease with medical photography of up to 5 target lesions, which will be chosen by the investigator (refer to Study Instructions).

12. Obtain a unilateral bone marrow biopsy/aspirate unless the patient's most recent bone marrow biopsy is negative for lymphoma involvement.
13. Obtain a 12-lead electrocardiogram (ECG). Repeat ECG during study only if clinically indicated.
14. Perform a comprehensive physical examination.
15. Assess and record ECOG Performance Status.

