8.5 Efficacy Endpoints

8.5.1 Progression-free Survival

The stratified log-rank test will be the primary method used to test the hypothesis that pralatrexate extends PFS relative to observation. In addition, the stratified Cox regression model will be used to calculate the PFS HR, along with the 95% CI. Strata used in these analyses will be those used for study randomization (as recorded using the interactive response technology [IRT]). Results of the unstratified Cox regression model (and log-rank test) will also be presented. The proportional hazards assumption of the Cox model will be assessed.

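### Adjusting PFS and OS for IPI and histology in one pre-specified Cox model would be a cheap gain in power; leaving them to exploratory models is not an error

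*SAP*

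**What the plan says.** SAP 8.5.1 and 8.5.2, like Protocol 15.7.1 and 15.7.2, make the stratified log-rank the primary test of PFS and OS and take the hazard ratio from the matching stratified Cox model. On the strata, SAP 8.5.1 says: "Strata used in these analyses will be those used for study randomization". The only such factor is investigator-assessed CR versus PR (SAP 3.1).

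Two further baseline factors are in hand before randomization. Protocol 10.1 has sites "Document IPI score at initial diagnosis", and Protocol 12.2.2 requires an independent pathology reviewer to confirm an eligible subtype first. SAP 4.4 lists IPI (score and components), histology in four groups, and region under the sentence "The following covariates will be considered in covariate-adjusted and other exploratory analyses". SAP 8.5.4 then explores the list in univariate and multivariate Cox models, and SAP 6.4 uses it for subgroups. The list, the histology grouping and the model class are therefore set. The IPI coding, an explicit treatment term and the standing of any adjusted result are not.

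SAP 3.2 sizes the trial "using a 2-sided stratified log-rank test at a 0.05 significance level". For OS it assumes "a true hazard ratio (HR) on OS of 0.73" and says that "a total of 385 OS events (deaths) will provide at least 80% power to show" an HR below 1. For PFS it says: "For a HR on PFS of 0.67", "a total of 280 PFS events (PD + deaths) will provide at least 80% power to show" the same.

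**The concern.** The protocol itself presents IPI as prognostic for death. Table 2.2 gives relative risks of 1.47 to 1.96 per factor. Table 2.3 gives 5-year OS in T-cell disease of 77%, 60%, 36% and 23% for 0, 1, 2 and 3 factors. In a proportional-hazards analysis, leaving out a prognostic baseline factor pulls the estimated hazard ratio toward 1 with almost no saving in standard error, so the test is weaker than the data allow. The stakes are higher than usual because a non-significant PFS result stops the study and success requires both endpoints (SAP 3.3).

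The second issue is pre-specification. With IPI usable as a score or as components, and with univariate and multivariate models both planned, an adjusted treatment effect could be chosen from several after the data are seen. It would then carry little weight.

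**Working it through.** **1. The plan's own figures.** Inputs from SAP 3.2: 2:1 allocation, two-sided 0.05, 385 deaths at HR 0.73, 280 PFS events at HR 0.67. By Schoenfeld's formula, power = Φ(√(d × 2/3 × 1/3) × |ln HR| − 1.96).

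- OS: √(385 × 2/9) = 9.250; × 0.3147 = 2.911; − 1.96 = 0.951; power **82.9%** (357 deaths suffice for 80%). At the final nominal level of 0.046 it is 82.0%. Over the three OS looks, by simulation, it is 82.5%.
- PFS: √(280 × 2/9) = 7.888; × 0.4005 = 3.159; − 1.96 = 1.199; power **88.5%** (221 events suffice for 80%).

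Both statements of at least 80% hold.

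**2. The IPI gradient.** Under exponential survival the log hazard is ln(−ln S₅). Relative to two factors, Table 2.3 gives:

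- 0 factors: ln(0.261/1.022) = −1.36
- 1 factor: ln(0.511/1.022) = −0.69
- 2 factors: 0
- 3 factors: ln(1.470/1.022) = +0.36

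I assumed a mix of 5/15/35/45% for 0, 1, 2 and 3 or more factors, consistent with the protocol's figure of about 80% at IPI 2 or higher (Protocol 2.3). The log-hazard SD is then 0.47.

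**3. Simulation.** 3,000 trials per scenario: 549 patients, blocks of 3 within CR/PR, uniform accrual over 54 months, exponential times, cut at 385 deaths or 280 PFS events, one two-sided 0.05 test. Assumptions not in the documents: PR versus CR hazard ratio 1.7, control median OS 28 months, histology mix 40/5/15/40%, assumed histology log hazard ratios where used, no dropout. A PR share of 22% was taken from the response rates in SAP 3.2. Monte Carlo error is about 0.7 points per power figure. Here 0.73 and 0.67 are effects conditional on the covariates. The adjusted model is a CR/PR-stratified Cox model with IPI (4 levels) and histology (4 levels).

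| Scenario (log-hazard SD) | OS planned → adjusted | PFS planned → adjusted |
|---|---|---|
| Not prognostic (0) | 83.4 → 83.2% | 90.6 → 90.4% |
| Half IPI gradient, small histology effect (0.25) | 81.9 → 83.9% | 88.5 → 90.0% |
| Full IPI gradient only (0.47) | 78.1 → 84.4% | 83.6 → 89.7% |
| Full gradient plus assumed histology effect (0.52) | 76.4 → 84.9% | 82.8 → 90.4% |

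With no covariate effect the simulation runs slightly above the formula (PFS 90.6% against 88.5%), so compare within rows.

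**4. Mechanism.** OS, full IPI gradient:

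- Planned: HR 0.748, SE 0.1065, Z = 0.290/0.1065 = 2.73.
- Adjusted: HR 0.726, SE 0.1076, Z = 0.320/0.1076 = 2.98.

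The gain comes from the hazard ratio moving away from 1, not from a smaller SE. The ratio of Z values is 1.092.

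**5. The other reading.** If 0.73 and 0.67 are the effects in the planned test, planned power stays at 82.9% and 88.5%. Scaling Z by the simulated ratio gives adjusted power for OS/PFS of 84.8%/90.1% at SD 0.25 and 88.8%/93.2% at SD 0.47. For the last OS figure: 2.911 × 1.092 = 3.179; − 1.96 = 1.219.

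**6. Extra strata instead of covariates.** Stratifying by CR/PR × IPI × histology (2 × 4 × 4 = 32 cells) loses power when the factors are not prognostic: OS 83.4 → 80.2%, PFS 90.6 → 84.6%.

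**The case against.** A log-rank test stratified by the randomization factor is valid, conventional, and the test on which the sample size rests. That stands. Three stronger conclusions that a reader might draw are not supported.

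- *The trial is underpowered.* OS power below 80% (76 to 78%) appears only if 0.73 is taken as conditional on IPI and the full Table 2.3 gradient holds. SAP 3.2 ties 0.73 to the stratified log-rank, which does not condition on IPI. On that reading nothing promised is lost.
- *IPI and histology are strongly prognostic in these patients.* Table 2.3 describes T-cell patients generally, not CHOP responders. It also shows CR falling from 82% to 35% across 0 to 3 factors, so part of the IPI effect runs through response. Response is an entry criterion, and CR/PR is already the stratifier. With the mix above, about 72% of the log-hazard variance (0.162 of 0.224) comes from patients with 0 or 1 factor. Eligibility removes some of these: ALK-positive ALCL with IPI below 2 and CR is excluded. For histology the plan says only that outcomes vary by subtype.
- *Adjustment costs nothing.* The protocol names the log-rank as primary, and OS monitoring includes a futility bound at HR 1.05 (SAP 3.3), so a new primary test is more than a SAP edit.

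These points shrink the expected gain and make it uncertain. They do not remove it or make covariate adjustment harmful. The ALK-positive exclusion also suggests that the sponsor regards IPI and histology as informative even in complete responders, though it does not quantify what remains.

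**Conclusion.** This is a low-cost efficiency and pre-specification improvement, not a mistake in the plan. Pre-specified covariate adjustment gains about 0 points of power if the factors carry no information in responders, 1.5 to 2 points at half the Table 2.3 gradient, and 5 to 6 points at the full IPI gradient. The last two ranges hold approximately under either reading of the design hazard ratios. Where the factors are uninformative, the simulated loss is 0.2 points, within Monte Carlo error. The last row of the table shows larger gains, but they rest on histology effects that I assumed. The size depends mainly on the IPI gradient among CHOP responders after allowing for CR/PR, which the documents do not give. A joint power figure for PFS and OS cannot be derived either, because their correlation is not stated.

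**What to change.** Before unblinding, which in this open-label trial means before any efficacy comparison by arm, write one model into SAP 8.5.1 and 8.5.2: a Cox model stratified by CR/PR with a treatment term, IPI in fixed categories (for example 0-1, 2, 3, 4-5) and the four SAP 4.4 histology groups. Enter IPI and histology as covariates, not as extra strata. Give missing IPI its own category, since the documents state no expected missing rate.

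Preferred use: take the primary test and hazard ratio from this model, apply the same model at every OS look and to the 1.05 futility bound, and report the stratified log-rank as supportive. This also needs a wording amendment to Protocol 15.7.1 and 15.7.2, matching changes wherever the log-rank is named as primary, and OS monitoring rules re-expressed for the model.

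Minimum use: keep the log-rank primary and name this single model as the key supportive analysis of PFS and OS. That is SAP wording only.

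In either case the adjusted hazard ratio is conditional on IPI and histology and will differ from the CR/PR-stratified one even without confounding. The report should say so. Coding and missing-data rules must be settled in advance. No new data collection is needed.

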5 ABBREVIATIONS AND DEFINITIONS

5.1 Abbreviations

AE	adverse event
ALCL	anaplastic large cell lymphoma
ATC	Anatomical Therapeutic Chemical
AUC	area under the curve
CHOP	cyclophosphamide, doxorubicin, vincristine, and prednisone
CI	confidence interval
CM	concomitant medication
C _{max}	maximum concentration
CR	complete response
CRT	case report tabulations
CTCAE	Common Terminology Criteria for Adverse Events
DMC	Data Monitoring Committee
ECG	electrocardiogram
ECOG	Eastern Cooperative Oncology Group
ESHAP	etoposide, methylprednisolone, cytarabine, and cisplatin
FAS	full analysis set
FFS	failure-free survival
HR	hazard ratio
IM	intramuscularly
IPD	important protocol deviation
IPI	International Prognostic Index
IRT	interactive response technology
IV	intravenous
IWC	International Workshop Criteria
K-M	Kaplan-Meier
m ²	square meter
MedDRA	Medical Dictionary for Regulatory Activities
mg	milligram
NaCl	sodium chloride
ORR	objective response rate
OS	overall survival
PD	progressive disease

PDX	(RS)-10-propargyl-10-deazaaminopterin (pralatrexate)
PET	positron emission tomography
PFS	progression-free survival
PK	pharmacokinetic(s)
po	by mouth
POPPK	population PK
PR	partial response
PTCL	peripheral T-cell lymphoma
PTCL-U	peripheral T-cell lymphoma unspecified
q	every
qd	once a day
SAE	serious adverse event
SD	stable disease
SOC	system organ class
$t_{1/2}$	half-life
TLGs	tables, listings, and graphs
WHODRUG	World Health Organization Drug

5.2 Definitions

Screening Phase

The screening phase is the period between signing of informed consent and randomization.

Baseline

For efficacy assessments, baseline is defined as the last assessment prior to randomization. For safety assessments, baseline is defined as the last assessment prior to study day 1.

Study Day 1

Study day 1 is defined as the treatment start date. By convention, when known, assessments that occur on the same date as the treatment start date but that occur before treatment will be assigned as study day 0; those occurring in the same day but after treatment start will be assigned as study day 1. For patients randomized to the Observation Arm, study day 1 will be assigned to all patients who do not withdraw from the study prior to 3 days post-randomization, and will be equal to the randomization date plus 3 days.

Cycle

For patients randomized to the Pralatrexate Arm, a cycle will be calculated as the time from the first administration of pralatrexate for the given cycle to the day before the first administration of the subsequent cycle. The last cycle for a patient will be calculated as the time from the first administration of protocol-specified treatment for the given cycle plus 4 weeks or to the last dose administered within the cycle, whichever is longer.

Complete Response

CR is defined based on the IWC.¹¹ The same imaging method(s) used to document disease pre-randomization are to be used for post-randomization response assessments.

Partial Response

PR is defined based on the IWC.¹¹ The same imaging method(s) used to document disease pre-randomization are to be used for post-randomization response assessments.

Objective Response

Objective response is defined as a tumor response assessment of either CR or PR based on IWC.¹¹ The same imaging method(s) used to document disease during screening are to be used for subsequent response assessments.

Stable Disease

SD is defined using IWC.¹¹

Progressive Disease

PD is defined using IWC.¹¹

Progression-free Survival Time

PFS time is calculated as the number of days from randomization to the date of objective documentation of PD or death, regardless of cause (PD date/death date - date of randomization + 1). Patients who are alive without a disease response assessment of PD will be censored at their last disease assessment date or the date of randomization, whichever is later. Date of progression will not be imputed for patients with missing tumor assessment(s) before an assessment of PD. Patients who withdraw from treatment prior to PD without withdrawing consent will be followed for disease status whenever possible, even if subsequent therapy, including transplant, has been initiated prior to documented PD per central review at least until the first interim analysis. Patients who have not died and who have no response assessments after baseline will be censored at randomization.

Overall Survival Time

OS time is calculated as the number of days from randomization to death (date of death - date of randomization + 1). Patients who have not died (no record of death) or are lost to follow-up will be censored at the date of last contact. Patients who withdraw from study visit participation will be followed for survival status. OS will be reported in months.

Treatment-emergent Adverse Event

A treatment-emergent AE is defined as an AE that occurs on or after study day 1 and that is a higher grade than was present just prior to study day 1.

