## 10.4 Pralatrexate Arm Procedures

### 10.4.1 Pralatrexate Cycle 1, Dose 1

The following evaluations and procedures must take place within 3 days following randomization and prior to treatment initiation (pralatrexate cycle 1, dose 1), unless otherwise noted below:

1. Record current medications including compliance with vitamin supplementation administered from 7 days prior to randomization (see [Section 13](#)).
2. Assess and record B symptoms .
3. Record study-procedure-related AEs and attribution (see <http://ctep.cancer.gov/reporting/ctc.html>).
4. Record weight in kilograms (kg), height in centimeters (cm) and calculate BSA. The patient's weight and BSA, to calculate the volume of the pralatrexate dose may be assessed up to 7 days prior to cycle 1, dose 1.
5. Local laboratory: Collect pre-injection blood for hematology and chemistry (including baseline LDH) (see [Section 12.1](#)). If any of the laboratory eligibility criteria are no longer met at this time, delay treatment for up to 1 week until these values return to the specified parameters, as follows: ANC  $\geq 1000/\mu\text{L}$ , platelet count  $\geq 100,000/\mu\text{L}$ , total bilirubin  $\leq 1.5 \text{ mg/dL}$ , AST and ALT  $\leq 2.5 \times \text{ULN}$  (AST/ALT  $< 5 \times \text{ULN}$  if documented hepatic involvement with lymphoma), creatinine  $\leq 1.5 \text{ mg/dL}$  or calculated creatinine clearance  $\geq 50 \text{ mL/min}$ .
6. Collect pre-injection blood sample for PK (see [Section 12.2.1](#)). PK sampling will be performed at cycle 1, dose 1 until samples have been obtained on 245 patients. Obtain samples until notified by Allos or designee.
7. Administer pralatrexate IV push over a minimum of 30 seconds up to a maximum of 5 minutes.
8. Collect blood samples for PK at the end of injection and at 8 and 24 hours post-injection (see [Section 12.2.1](#)). PK sampling will be performed at cycle 1, dose 1 until samples have been obtained on 245 patients. Obtain samples until notified by Allos or designee.

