## 10.5 Observation Arm Procedures

### 10.5.1 Observation Arm: Baseline Visit

The following evaluations and procedures must take place within 3 days following randomization, unless otherwise noted below:

1. Record current medications including compliance with vitamin supplementation administered from 7 days prior to randomization (see [Section 13](#)).
2. Assess and record B symptoms.
3. Record study-procedure-related AEs and attribution (see <http://ctep.cancer.gov/reporting/ctc.html>).
4. Record weight in kg and height in cm up to 7 days prior to baseline visit.
5. Local laboratory: Collect blood for hematology and chemistry (including baseline LDH) (see [Section 12.1](#)).

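### SAP 5.2 places Observation Arm study day 1 on the last permitted day of that arm's Baseline Visit, so safety data from a compliant day-3 visit are classed as post-baseline

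*SAP*

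**What the plan says.** SAP 5.2 (Definitions) sets the safety baseline rule for both arms: "For safety assessments, baseline is defined as the last assessment prior to study day 1".

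Study day 1 itself differs by arm. The general rule is "Study day 1 is defined as the treatment start date", with a same-date convention, applied when the timing is known: "assessments that occur on the same date as the treatment start date but that occur before treatment will be assigned as study day 0". For Observation Arm patients who have not withdrawn by then, study day 1 is a fixed calendar date: "and will be equal to the randomization date plus 3 days".

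Protocol 10.5.1 describes the Observation Arm Baseline Visit. Its procedures "must take place within 3 days following randomization, unless otherwise noted below", and Appendix 2 gives the same window. They include B symptoms and blood tests; the laboratory item begins "Local laboratory: Collect blood for hematology and chemistry (including baseline LDH". In the Pralatrexate Arm, Protocol 10.4.1 sets the same three-day window but also requires the evaluations to precede the first dose.

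**The concern.** The two documents meet on one date. The last day on which an Observation patient may attend the Baseline Visit is also that patient's study day 1. Baseline must come before study day 1, so a patient who attends on the last permitted day, in full compliance, has a Baseline Visit whose results cannot serve as baseline. The protocol names the visit, and the LDH drawn at it, as baseline, so the SAP rule defeats the purpose of the visit for these patients.

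The arms are then handled differently. A Pralatrexate patient assessed and dosed on the same date keeps the pre-dose values as baseline. An Observation patient assessed on study day 1 falls back to screening. The summaries exposed, all in SAP 8.6, are laboratory change from baseline, post-baseline maximum and minimum, CTCAE grade shifts, and time to onset or worsening of B symptoms. Changes in laboratory values are one of the two safety endpoints in SAP 4.3, and safety is the study's secondary objective.

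**Working it through.** The plan gives no figure to reproduce on this point. The check is a day count, followed by a range for the number of patients.

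**Inputs**
- Observation study day 1 = randomization + 3 (SAP 5.2).
- Safety baseline = latest assessment dated before study day 1 (SAP 5.2).
- Permitted Observation Baseline Visit days: randomization + 0 to + 3 (Protocol 10.5.1, Appendix 2).
- Screening laboratory tests and B symptoms: up to 21 days before randomization (Protocol 10.1).
- Planned Observation Arm size: 183 (SAP 3.2).

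**Step 1: classify each permitted visit day.** A visit on day *d* supplies baseline only if *d* < 3.

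| Observation visit | Relation to study day 1 | Classed as |
|---|---|---|
| Randomization + 0 | 3 days before | baseline |
| Randomization + 1 | 2 days before | baseline |
| Randomization + 2 | 1 day before | baseline |
| Randomization + 3 | same date | post-baseline |

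**Step 2: does the study-day-0 convention rescue day 3?** It divides assessments on the treatment start date into those before and those after treatment. For Observation the SAP supplies a calendar date and no event on that date, so there is nothing to divide by. The Pralatrexate Arm has the dose. Its pre-dose assessments fall either on an earlier date or, when the order is known, on study day 0. Both count as baseline.

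**Step 3: age of the replacement baseline.** The oldest permitted screening value lies 21 + 3 = 24 days before study day 1. That is a ceiling; a later screening sample is closer.

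**Step 4: which data move.** Only assessments made both at screening and at the Baseline Visit: hematology, chemistry including LDH, and B symptoms. A screening value exists for each, so baseline is displaced, not lost. The day-3 value joins the post-baseline set, and a B symptom first noted then would count as an onset on study day 1. ECOG status and ECG are taken at screening and do not move. SAP 5.2 ties efficacy baseline to randomization, so response is untouched, and PFS and OS are timed from randomization.

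**Step 5: how many patients.** The documents give no distribution of visit days, so these are assumptions:
- even spread over days 0 to 3: 183 / 4 = 45.75, about 46;
- even spread over days 1 to 3: 183 / 3 = 61;
- logical limits: 0 (no visits on day 3) to 183 (all visits on day 3).

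**The case against.** The strongest reply is that the intent is plain. The protocol speaks of observation as a study treatment (7.3, 11.1) and of its initiation (7.1), and the study-day-0 sentence is not expressly confined to one arm. A sensible programmer would treat the Baseline Visit as baseline. The intent is indeed clear, but the rule still gives the opposite result, because Observation has no before and after on study day 1. In an open-label trial such a choice should be written down before the data are reviewed.

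Other parts of the reply stand and limit the point:

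- A reader might infer that the problem can arise in the Observation Arm only. The SAP applies study day 0 only when the timing is known and does not say what happens otherwise. A Pralatrexate sample on the dosing date with no recorded order is equally unresolved.
- A reader might take 46 as the expected number of patients. It is one assumption within a range of 0 to 183.
- A reader might infer that count recovery after CHOP would show as on-study change under observation but not under pralatrexate. The documents do not support that for the arm as a whole. Visits on days 0 to 2 are handled as intended. Entry limits (Protocol 8.3: ANC at least 1000/µL, platelets at least 100,000/µL) restrict how low a screening count can be. Recovery after day 3 appears as change under either baseline.
- Observation laboratory tests continue every 28 days for up to 2 years (Protocol 10.5.3). One extra early value will seldom set a patient's maximum or minimum, and it is the last value only if no later test exists. For B symptoms, baseline status changes only if it differed between screening and day 3.

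**Conclusion.** Wrong as written; minor severity. This is a stated rule that misclassifies compliant data, not merely a missing detail. That conclusion rests on reading SAP 5.2 literally and does not depend on how many visits fall on day 3. The size does depend on it: about 46 or 61 of 183 patients under the two even-spread assumptions, with 0 to 183 possible. For each affected patient the baseline is a screening value at most 24 days before study day 1. The consequences are confined to safety summaries: laboratory change from baseline, post-baseline extremes, grade shifts and B-symptom onset. The difference between arms holds where the Pralatrexate Arm's pre-dose timing is known. Nothing here bears on PFS, OS or response, and the documents do not show that any safety conclusion would change.

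**What to change.** Leave Observation study day 1 at randomization + 3 days and add one sentence to SAP 5.2: *Observation Arm Baseline Visit assessments made on the date of study day 1 are assigned to study day 0 and count as the safety baseline.* This gives the arm the counterpart of the pre-dose convention.

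Moving study day 1 to the visit date would also remove the overlap, but it is broader than needed. SAP 5.2 starts the treatment-emergent adverse event window at study day 1, so the window would shift for every Observation patient seen on days 0 to 2 and would depend on site scheduling. It would also part study day 1 from the 3-day rule for the safety set (SAP 6.2): a patient seen on day 0 who discontinued on day 2 would have a study day 1 yet be outside that set.

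The cost is one SAP sentence and one derivation rule. No new data, protocol amendment or change to patient care is needed.
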